## 8. ANALYSIS POPULATIONS

The following analysis sets/populations will be used in this trial:

- Safety population: include all subjects who receive at least one dose of IP. The safety population is the population used for all safety analyses.
- Full analysis set (FAS) – All randomized subjects who receive at least one dose of investigational product and have at least one post dose efficacy assessment. The FAS population will be the primary population for the efficacy analyses
- Per Protocol (PP) population: include subjects in the FAS population who complete the study without any major protocol violations that are considered likely to affect the efficacy analysis outcomes of the study. Major protocol violations will include but not be restricted to the following:
  - Failure to meet the inclusion/exclusion criteria that are considered likely to affect the efficacy analysis outcomes of the study
  - Randomization error

- Usage of any prohibited concomitant medications or procedures
- Failure to have Week 24 assessment within the allowable window for either of the co-primary endpoints
- Failure to be compliant with treatment regimen

Additional criteria may be added to determine PP population. The composition of the PP population will be determined and documented in blind reviews of the database conducted prior to unblinding the study database. Subjects who used rescue medications or who discontinued due to unsatisfactory therapeutic effect will be included in the PP population. These subjects will be considered as treatment failures (i.e., non-responder for both PASI-75 and IGA) for all time points after the initiation of rescue medications or subject discontinuation.

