The imputation of missing post-baseline BSA, PSSI final score, NAPSI, and NRS scores will be performed using a similar method as described for PASI. The imputation of missing post-baseline PP PGA scores will be performed using a similar method as described for IGA. A pre-specified seed number of 132138 will be used in all imputation procedures. No imputation will be done to the health-related quality of life endpoints or safety endpoints.

- **Observed cases (OC)**: No imputation will be performed, only observed values will be analyzed.
- **m-NRI (response endpoint only)**: Subjects who used rescue medications or discontinued due to unsatisfactory therapeutic effect are considered as treatment failures (i.e., non-responder) for all time points after the initiation of rescue medications or subject discontinuation. For example, if a subject discontinued due to lack of efficacy, all visits

after the last planned visits will be imputed to non-responders. If a subject used rescue medication during the study, all visits after the start of the rescue medication will be imputed to non-responders regardless if the subject had an assessment or not. Other subjects with missing data will be kept as missing (i.e., no imputation). Discontinuation due to unsatisfactory therapeutic effect will be identified by discontinuation reason = "Other" with a comment "lack of efficacy" on the eCRF.

- **LOCF:** The last observed value will be carried forward for any subsequent missing values. Baseline values will not be carried forward.

A summary of the imputation methods for all efficacy endpoints is shown below:

Endpoint	Analysis Population	Imputation Methods
PASI-75 at Week 24	FAS	MI, m-NRI, LOCF, OC
	PP	m-NRI
IGA score of clear or almost clear at Week 24	FAS	MI, m-NRI, LOCF, OC
	PP	m-NRI
Change from Baseline and percent change from Baseline in PASI Total Score by Visit	FAS	MI, LOCF, OC
	PP	OC
PASI-50 and PASI-75 by Visit	FAS	MI, m-NRI, LOCF, OC
	PP	m-NRI
IGA score of clear or almost clear by Visit	FAS	MI, m-NRI, LOCF, OC
	PP	m-NRI
Change from Baseline and percent change from Baseline in BSA by Visit	FAS	MI, LOCF, OC
	PP	OC
Change from Baseline in NPSI by Visit	FAS	MI, LOCF, OC
	PP	OC
Change from Baseline in PSSI by Visit	FAS	MI, LOCF, OC
	PP	OC
Change from Baseline in PP PGA by Visit	FAS	MI, LOCF, OC
	PP	OC
Change from Baseline in NRS by Visit	FAS	MI, LOCF, OC
	PP	OC
Time to PASI-75	FAS	OC
Time to achieving an IGA score of clear or almost clear	FAS	OC
QIDS-SR 16	FAS	OC

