m-NRI: subjects who used rescue medications or discontinued due to unsatisfactory therapeutic effect are considered as treatment failures for all time points after the initiation of rescue medications or subject discontinuation.

[1] n = Number of responders at Week 24. N = Number of subjects with a Week 24 assessment.

[1] Logistic model includes treatment group, baseline BMI, and pooled analysis center as factors.

Generated on XX/XX/XX:XXXX by XXXXX / Uses: XXXX / Reference: Listings XXXX

< Repeat Table 14.2.1.1.2 for >

Table 14.2.1.1.3: Analysis of Co-Primary Efficacy Outcome, Sensitivity Analysis  
PASI-75 Response Rate at Week 24  
Full Analysis Set, m-NRI

Table 14.2.1.1.4: Analysis of Co-Primary Efficacy Outcome, Sensitivity Analysis  
PASI-75 Response Rate at Week 24  
Full Analysis Set, LOCF

*Programming note: modify the Note accordingly for the definition of LOCF*

Table 14.2.1.1.5: Analysis of Co-Primary Efficacy Outcome, Sensitivity Analysis  
PASI-75 Response Rate at Week 24  
Full Analysis Set, OC

*Programming note: modify the Note accordingly for the definition of OC*

Table 14.2.1.2.1: Analysis of Co-Primary Efficacy Outcome  
IGA Treatment Success Rate at Week 24  
Full Analysis Set, Multiple Imputation

	PPC-06 400 mg QD (N=XX)	PPC-06 400 mg BID (N=XX)	PPC-06 600 mg BID (N=XX)	Placebo (N=XX)
IGA Treatment Success Rate (%) [1]	XX.X	XX.X	XX.X	XX.X
Logistic Regression [2]				
Log (Odds Ratio) (SE), PPC-06 vs. Placebo	X.XX (X.XX)	X.XX (X.XX)	X.XX (X.XX)	
Odds Ratio	X.XX	X.XX	X.XX	
Odds Ratio 95% CI	X.XX, X.XX	X.XX, X.XX	X.XX, X.XX	
p-value [3]	0.XXXX	0.XXXX	0.XXXX	
Pairewise Comparisons Between PPC-06 Treatments				
Log (Odds Ratio) (SE), PPC-06 vs. PPC-06 600 mg BID	X.XX (X.XX)	X.XX (X.XX)		
Odds Ratio	X.XX	X.XX		
Odds Ratio 95% CI	X.XX, X.XX	X.XX, X.XX		
p-value [3]	0.XXXX	0.XXXX		
Log (Odds Ratio) (SE), PPC-06 vs. PPC-06 400 mg BID	X.XX (X.XX)			
Odds Ratio	X.XX			
Odds Ratio 95% CI	X.XX, X.XX			
p-value [3]	0.XXXX			

Note: IGA= Investigator's Global Assessment; SE=Standard Error; CI=Confidence Interval. IGA Treatment Success is defined as achieving an IGA score of clear or almost clear (IGA score 0 or 1) at the end of Week 24.

[1] Average IGA treatment success rate over 50 imputed datasets.

[2] Logistic model includes treatment group, baseline BMI, and pooled analysis center as factors.

[3] p-value is for null hypothesis that the combined log (Odds Ratio) equals 0.

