Generated on XX/XX/XX:XXXX by XXXXX / Uses: XXXX / Reference: Listings XXXX

Table 14.2.1.2.2: Analysis of Co-Primary Efficacy Outcome  
IGA Treatment Success Rate at Week 24  
PP Population, m-NRI

	PPC-06 400 mg QD (N=XX)	PPC-06 400 mg BID (N=XX)	PPC-06 600 mg BID (N=XX)	Placebo (N=XX)
IGA Treatment Success Rate, n / N (%) [1]	XX / XX (XX.X)	XX / XX (XX.X)	XX / XX (XX.X)	XX / XX (XX.X)
Logistic Regression [2]				
Odds Ratio, PPC-06 vs. Placebo	X.XX	X.XX	X.XX	
Odds Ratio 95% CI	X.XX, X.XX	X.XX, X.XX	X.XX, X.XX	
p-value	0.XXXX	0.XXXX	0.XXXX	
Pairwise Comparisons Between PPC-06 Treatments				
Odds Ratio, PPC-06 vs. PPC-06 600 mg BID	X.XX	X.XX		
Odds Ratio 95% CI	X.XX, X.XX	X.XX, X.XX		
p-value	0.XXXX	0.XXXX		
Odds Ratio, PPC-06 vs. PPC-06 400 mg BID	X.XX			
Odds Ratio 95% CI	X.XX, X.XX			
p-value	0.XXXX			

Note: IGA= Investigator's Global Assessment; m-NRI=modified non-responder imputation; CI=Confidence Interval. IGA Treatment Success is defined as achieving an IGA score of clear or almost clear (IGA score 0 or 1) at the end of Week 24.

[1] n = Number of responders at Week 24. N = Number of subjects with a Week 24 assessment.

[2] Logistic model includes treatment group, baseline BMI, and pooled analysis center as factors.

Generated on XX/XX/XX:XXXX by XXXXX / Uses: XXXX / Reference: Listings XXXX

< Repeat Table 14.2.1.2.2 for >

Table 14.2.1.2.3: Analysis of Co-Primary Efficacy Outcome, Sensitivity Analysis  
IGA Treatment Success Rate at Week 24  
Full Analysis Set, m-NRI

Table 14.2.1.2.4: Analysis of Co-Primary Efficacy Outcome, Sensitivity Analysis  
IGA Treatment Success Rate at Week 24  
Full Analysis Set, LOCF

*Programming note: modify the Note accordingly for the definition of LOCF*

Table 14.2.1.2.5: Analysis of Co-Primary Efficacy Outcome, Sensitivity Analysis  
IGA Treatment Success Rate at Week 24  
Full Analysis Set, OC

*Programming note: modify the Note accordingly for the definition of OC*

Table 14.2.1.3.1: Analysis of Co-Primary Efficacy Outcome, Subgroup Analysis  
PASI-75 Response Rate at Week 24 by Baseline hsCRP  
Full Analysis Set, Multiple Imputation  
[Baseline hsCRP < 5mg/L][Baseline hsCRP >= 5mg/L]

	PPC-06 400 mg QD (N=XX)	PPC-06 400 mg BID (N=XX)	PPC-06 600 mg BID (N=XX)	Placebo (N=XX)
PASI-75 Response Rate				
N	XX	XX	XX	XX
Response Rate [1]	XX.X	XX.X	XX.X	XX.X
Logistic Regression [2]				
Log (Odds Ratio) (SE), PPC-06 vs. Placebo	X.XX (X.XX)	X.XX (X.XX)	X.XX (X.XX)	

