	PPC-06 400 mg QD (N=XX)	PPC-06 400 mg BID (N=XX)	PPC-06 600 mg BID (N=XX)	Placebo (N=XX)
Week 8				
N	XX	XX	XX	XX
% [1]	XX.X	XX.X	XX.X	XX.X
Logistic Regression [2]				
Log (Odds Ratio) (SE), PPC-06 vs. Placebo	XX.X (XX.X)	XX.X (XX.X)	XX.X (XX.X)	
Odds Ratio	XX.X	XX.X	XX.X	
Odds Ratio 95% CI	XX.X, XX.X	XX.X, XX.X	XX.X, XX.X	
p-value [3]	X.XXXX	X.XXXX	X.XXXX	

<Repeat for other visits: Week 12, Week 16, Week 20, and Week 24>

Note: PASI=Psoriasis Area and Severity Index; SE=Standard Error; CI=Confidence Interval. PASI-50 Treatment Success is defined as achieving a reduction of 50% or greater from Baseline.

[1] Average PASI-50 response rate over 50 imputed datasets.

[2] Logistic model includes treatment group, baseline BMI, and pooled analysis center as factors.

[3] p-value is for null hypothesis that the combined log (Odds Ratio) equals 0.

Generated on XX/XX/XX:XXXX by XXXXXX / Uses: XXXX / Reference: Listing XXXX

Table 14.2.2.2.2: Analysis of Secondary Efficacy Outcome  
PASI-50 Response Rate by Visit  
Double-Blind Treatment Period  
Full Analysis Set, LOCF

	PPC-06 400 mg QD (N=XX)	PPC-06 400 mg BID (N=XX)	PPC-06 600 mg BID (N=XX)	Placebo (N=XX)
Baseline				
n / N (%)	XX/XX (XX.X)	XX/XX (XX.X)	XX/XX (XX.X)	XX/XX (XX.X)
Week 8				
n / N (%)	XX/XX (XX.X)	XX/XX (XX.X)	XX/XX (XX.X)	XX/XX (XX.X)
Logistic Regression [1]				
Odds Ratio, PPC-06 vs. Placebo	XX.X	XX.X	XX.X	
Odds Ratio 95% CI	XX.X, XX.X	XX.X, XX.X	XX.X, XX.X	
p-value	X.XXXX	X.XXXX	X.XXXX	

<Repeat for other visits: Week 12, Week 16, Week 20, and Week 24>

Note: PASI=Psoriasis Area and Severity Index; LOCF=Last Observation Carried Forward; CI=Confidence Interval. PASI-50 Treatment Success is defined as achieving a reduction of 50% or greater from Baseline. n = Number of responders at each visit. N = Number of subjects available for analysis at each visit.

[1] Logistic model includes treatment group, baseline BMI, and pooled analysis center as factors.

Generated on XX/XX/XX:XXXX by XXXXX / Uses: XXXX / Reference: Listing XXXX

<Repeat for tables:>

Table 14.2.2.2.3: Analysis of Secondary Efficacy Outcome  
PASI-50 Response Rate by Visit in the Double-Blind Treatment Period  
Full Analysis Set, m-NRI

*Programming note: modify the Note accordingly for the definition of m-NRI*

Table 14.2.2.2.4: Analysis of Secondary Efficacy Outcome  
PASI-50 Response Rate by Visit in the Double-Blind Treatment Period  
Full Analysis Set, OC

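### The co-primary m-NRI tables take N as the subjects assessed at Week 24, so failures imputed without an assessment drop out of the printed response rates

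*SAP*

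**What the plan says.** **The imputation rule.** SAP Section 9 defines m-NRI for the response endpoints. Rescue users and subjects who stop for lack of efficacy are "considered as treatment failures (i.e., non-responder) for all time points after the initiation of rescue medications or subject discontinuation". For rescue users it adds that later visits are "imputed to non-responders regardless if the subject had an assessment or not". All remaining gaps stay open: "Other subjects with missing data will be kept as missing (i.e., no imputation".

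**The PP population.** SAP Section 8 excludes subjects who lack an in-window Week 24 assessment for either co-primary endpoint, but then makes an exception: "Subjects who used rescue medications or who discontinued due to unsatisfactory therapeutic effect will be included in the PP population". They count there as treatment failures. The imputation summary in Section 9 lists m-NRI as the only method for the co-primary endpoints in PP.

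**The table shells.** In Table 14.2.1.1.2 (PASI-75, PP) the general note restates the m-NRI rule, and footnote [1] beneath it reads "1] n = Number of responders at Week 24. N = Number of subjects with a Week 24 assessment". Table 14.2.1.2.2 (IGA, PP) has the same footnote. Both shells are repeated for FAS m-NRI (14.2.1.1.3 and 14.2.1.2.3) with no programming note. The LOCF and OC repeats do carry an instruction to adapt the note.

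**The by-visit shells.** Table 14.2.2.2.2 (PASI-50 by visit, repeated for m-NRI as 14.2.2.2.3) uses another denominator: "N = Number of subjects available for analysis at each visit".

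**The concern.** An imputed failure is by definition not a responder, so it never enters n. If the subject also has no Week 24 assessment, the footnote keeps that subject out of N as well. The failure that m-NRI was meant to count then has no effect on the printed rate.

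The conflict matters most in the PP tables. The exception in Section 8 brings in rescued and lack-of-efficacy subjects who would otherwise be excluded for want of a Week 24 assessment, and footnote [1] takes them out of the percentage again. No other PP rate is planned for the co-primary endpoints.

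The SAP also uses two denominators for one visit and one imputation method: PASI-50 at Week 24 under m-NRI follows the by-visit wording, while PASI-75 at Week 24 under m-NRI follows footnote [1]. The by-visit PASI-75 and IGA shells omit Week 24, so a rate on the wider denominator is not printed elsewhere for the co-primary endpoints.

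**Working it through.** **Inputs.** From SAP Section 7: 100 randomized per arm, 50% dropout, about 50 completers per arm, response 15% on placebo and 45% on PPC-06, two-sided 0.05, power at least 84%. Assumed: A = 50 subjects per arm with a Week 24 assessment (the planned completers), with the planned rates applying to them. Not in the documents: k, the number per arm imputed as non-responders without a Week 24 assessment.

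**The plan's own figure.** With n = 50 per arm, the pooled-variance formula gives (0.30 − 1.96 × √(2 × 0.30 × 0.70/50)) / √((0.15 × 0.85 + 0.45 × 0.55)/50) = (0.300 − 0.180)/0.0866 = 1.39, so power is 0.918 per endpoint. For two endpoints treated as independent, 0.918² = 0.842, which matches the stated 84%. The plan's power therefore rests on 50 assessed subjects per arm. The footnote does not affect it.

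**Effect of the footnote on a rate.** The printed rate is n/A. The m-NRI rate is n/(A+k). Their ratio is (A+k)/A, which is never below 1. The responders are 0.45 × 50 = 22.5 active and 0.15 × 50 = 7.5 placebo.

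| k | Factor | Active: printed → m-NRI | Placebo: printed → m-NRI |
|---|---|---|---|
| 0 | 1.0 | 45.0% → 45.0% | 15.0% → 15.0% |
| 5 | 1.1 | 45.0% → 40.9% | 15.0% → 13.6% |
| 10 | 1.2 | 45.0% → 37.5% | 15.0% → 12.5% |
| 20 | 1.4 | 45.0% → 32.1% | 15.0% → 10.7% |

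The ceiling is k = 50, where all planned dropouts are imputed failures and the factor is 2.0.

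**Effect on the difference between arms.** It depends on how k is split.

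- k = 15 in both arms: 22.5/65 − 7.5/65 = 34.6% − 11.5% = 23.1 points, against 30.0 printed.
- k = 5 active and 20 placebo: 22.5/55 − 7.5/70 = 40.9% − 10.7% = 30.2 points, against 30.0 printed. The crude odds ratio here rises from (22.5/27.5)/(7.5/42.5) = 4.64 to (22.5/32.5)/(7.5/62.5) = 5.77.

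Only the direction of the error in each arm's rate is certain.

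**The case against.** The strongest reply is that this is loose wording in a mock shell. The m-NRI definition stands in the same table note, SAP Section 11.1 ties denominators to the subjects suited to each analysis, and Listings 16.2.6.1.2 and 16.2.6.2 show m-NRI non-response rows at visits without a date. A programmer might well build N from those records. That may be the intention, but a general rule does not override a specific footnote. Nor can an assessment be read to include an imputed value, because the rescue rule in Section 9 itself separates the two.

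These limits on scope stand:

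- Some imputed failures remain in N. SAP Section 11.4 places assessments from Day 155 on, if within 15 days of the last dose, in the Week 24 window, so a late early termination visit counts. Rescued subjects may stay in the study and be assessed at Week 24.
- The clause about having an assessment or not covers rescue users only. Lack-of-efficacy discontinuers are covered by the general m-NRI rule and its own example.
- Dropouts for other reasons stay missing under m-NRI and are outside N on either definition.
- Lack of efficacy is not a listed withdrawal reason in Protocol Section 5.4. It is captured only as a comment under Other, so k could be small.

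Three stronger readings are tempting and are not supported:

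- **The m-NRI tables would nearly reproduce the observed-case tables.** Rescued subjects assessed at Week 24 count as failures under m-NRI and not under OC, and the documents do not say how many there will be.
- **Robustness of the treatment effect is overstated.** The second split above moves the difference and the crude odds ratio the other way.
- **The odds ratios and p-values are wrong.** The footnote governs the printed n/N, and nothing in the SAP applies it to the logistic model.

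**Conclusion.** The footnote contradicts SAP Sections 8 and 9 and should be corrected. Followed as written, it makes each arm's printed m-NRI rate equal to or higher than the rate the method defines, by (A+k)/A. With A assumed to be 50, that is 1.1 at k = 5, 1.2 at k = 10 and 1.4 at k = 20. At k = 0 there is no error. All sizes depend on k, which the documents do not supply, so they are illustrations and not estimates.

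The consequence is limited to printed rates in two sensitivity tables (FAS) and two supporting tables (PP). The primary FAS analysis by MI is unaffected. If the logistic model is fitted to the m-NRI data, its odds ratios and p-values are also unaffected, but the rates printed above them would rest on a different set of subjects whenever k is above zero.

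**What to change.** In Tables 14.2.1.1.2, 14.2.1.1.3, 14.2.1.2.2 and 14.2.1.2.3, define N as the number of subjects with an observed or m-NRI-imputed Week 24 response, and state that this is the set entering the logistic model. When the LOCF repeats (14.2.1.1.4 and 14.2.1.2.4) are adapted under their existing programming note, count observed or carried-forward responses in N. The OC repeats can keep the present wording.

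The cost is a footnote change in the shells, with no new data or analysis. The downside for the sponsor is that the printed m-NRI rates become less favourable or stay the same.

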### **12.8.2 Secondary Efficacy Analyses**

All secondary efficacy analyses will be performed on the FAS and PP populations.

The following categorical secondary efficacy endpoints will be summarized using the number and percentage of subjects within each category for each treatment group. A same logistic regression model as used for the primary endpoint will be performed. Each PPC-06 group will be compared to placebo separately as described in the primary analysis.

- Proportion of subjects who achieve PASI-50 and PASI-75 by visit in the Double-Blind Treatment Period
- Proportion of subjects who achieve an IGA score of clear or almost clear by visit in the Double-Blind Treatment Period

The observed values and change from baseline in PP PGA will be summarized as categorical endpoint using frequency counts and percentages. The change from baseline in severity categories will be compared between treatment groups using a Wilcoxon rank sum test.

The following continuous secondary efficacy endpoints will be summarized descriptively and analyzed using an Analysis of Covariance (ANCOVA) including factors for treatment, baseline

BMI, and pooled analysis center. Each PPC-06 group will be compared to placebo separately. The least square mean (LSM) difference, along with the 95% CI and p-value will be reported.

- Change from Baseline and percent change from Baseline in total PASI Score by visit in the Double-Blind Treatment Period
- Change from Baseline and percent change from Baseline in percent of affected BSA by Visit in the Double-Blind Treatment Period
- For applicable subjects, change from baseline in NAPSI of the target fingernail at Weeks 12, 16 and 24
- For applicable subjects, change from baseline by visit in PSSI in the Double-Blind Treatment Period
- Change from Baseline and percent change from Baseline in pruritus NRS score by Visit in the Double-Blind Treatment Period

The following time to event variables will be analyzed using the Kaplan-Meier (KM) method. Subjects who have not achieved treatment response by the last visit or discontinue the study will be censored at their last visit. The mean, 25th, 50th, and 75th percentile time to achieving a treatment success will be reported; log-rank test will be performed for the comparison between each PPC-06 arm and placebo.

- Time to achieving PASI-75 response
- Time to achieving IGA 0 or 1

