## 13.CHANGES FROM THE PROTOCOL AND PLANNED ANALYSES

Protocol states PP PGA will be analyzed using a similar method as NPSI, PSSI. The SAP summarizes PP PGA using frequency counts and percentages. Wilcoxon rank sum test will be used to compare the change from baseline in PP PGA between treatment groups.

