Change from Baseline in Psoriasis Scalp Severity Index (PSSI) Total Score by Visit  
Double-Blind Treatment Period  
Full Analysis Set, LOCF

	PPC-06 400 mg QD (N=XX)	PPC-06 400 mg BID (N=XX)	PPC-06 600 mg BID (N=XX)	Placebo (N=XX)
Baseline				
N	XX	XX	XX	XX
Mean (SD)	XX.X (XX.X)	XX.X (XX.X)	XX.X (XX.X)	XX.X (XX.X)
Median	XX	XX	XX	XX
Minimum, Maximum	XX, XX	XX, XX	XX, XX	XX, XX
Week 8				
N	XX	XX	XX	XX
Mean (SD)	XX.X (XX.X)	XX.X (XX.X)	XX.X (XX.X)	XX.X (XX.X)
Median	XX	XX	XX	XX
Minimum, Maximum	XX, XX	XX, XX	XX, XX	XX, XX
Change from baseline				
N	XX	XX	XX	XX
Mean (SD)	XX.X (XX.X)	XX.X (XX.X)	XX.X (XX.X)	XX.X (XX.X)
Median	XX	XX	XX	XX
Minimum, Maximum	XX, XX	XX, XX	XX, XX	XX, XX
Analysis of Covariance (ANCOVA) [1]				
LSM (SE)	XX.X (XX.X)	XX.X (XX.X)	XX.X (XX.X)	XX.X (XX.X)
LSM, 95% CI	XX.X, XX.X	XX.X, XX.X	XX.X, XX.X	XX.X, XX.X
LSM Difference (SE), PPC-06 vs. Placebo	XX.X (XX.X)	XX.X (XX.X)	XX.X (XX.X)	
95% CI	XX.X, XX.X	XX.X, XX.X	XX.X, XX.X	
p-value	X.XXXX	X.XXXX	X.XXXX	

<Repeat for Week12, Week16, Week20, Week24>

Note: This analysis excludes subjects with baseline PSSI score of 0. LOCF = Last Observation Carried Forward.

[1] ANCOVA model includes treatment as factor, baseline BMI and pooled analysis centers as covariates.

Generated on XX/XX/XX:XXXX by XXXXXX / Uses: XXXX / Reference: Listings XXXX

*Repeat for tables:*

Table 14.2.2.7.3: Analysis of Secondary Efficacy Outcome  
Change from Baseline in Psoriasis Scalp Severity Index (PSSI) Total Score by Visit  
Double-Blind Treatment Period  
Full Analysis Set, OC

*Programming note: Update footnote for the deflection of OC*

Table 14.2.2.7.4: Analysis of Secondary Efficacy Outcome  
Change from Baseline in Psoriasis Scalp Severity Index (PSSI) Total Score by Visit  
Double-Blind Treatment Period  
PP Population, OC

*Programming note: Update footnote for the deflection of OC*

Table 14.2.2.8.1: Analysis of Secondary Efficacy Outcome  
Change from Baseline in Palmoplantar Psoriasis Physician's Global Assessment (PP PGA) by Visit  
Double-Blind Treatment Period  
Full Analysis Set, Multiple Imputation

	PPC-06 400 mg QD (N=XX)	PPC-06 400 mg BID (N=XX)	PPC-06 600 mg BID (N=XX)
Wilcoxon Rank Sum Test p-value, PPC-06 vs. Placebo [1]			
Week 8	X.XXXX	X.XXXX	X.XXXX
Week 12	X.XXXX	X.XXXX	X.XXXX
Week 16	X.XXXX	X.XXXX	X.XXXX
Week 20	X.XXXX	X.XXXX	X.XXXX
Week 24	X.XXXX	X.XXXX	X.XXXX

Note: This analysis excludes subjects with baseline PP PGA score of 0.

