[1] Average based on 50 imputed datasets.

Generated on XX/XX/XX:XXXX by XXXXX / Uses: XXXX / Reference: Listings XXXX

[*Programming note: Use the following syntax to perform Wilcoxon Rank Sum test for MI*

```
Proc NPAR1WAY data=indata Wilcoxon hl;  
  By _imputation_;  
  Var Chg;  
  ODS OUTPUT WilcoxonTest=wilcox HodgesLehmann=hl;  
Run;
```

```
Proc Mianalyze data=hl;  
  Modeffects shift;  
  Stderr stderr;  
  ODS OUTPUT ParameterEstimates=stats;  
Run;
```

```
]
```

Table 14.2.2.8.2: Analysis of Secondary Efficacy Outcome  
Change from Baseline in Palmoplantar Psoriasis Physician's Global Assessment (PP PGA) by Visit  
Double-Blind Treatment Period  
Full Analysis Set, LOCF

	PPC-06 400 mg QD (N=XX)	PPC-06 400 mg BID (N=XX)	PPC-06 600 mg BID (N=XX)	Placebo (N=XX)
Baseline, n (%)				
1 - Almost clear	XX (XX.X)	XX (XX.X)	XX (XX.X)	XX (XX.X)
2 - Mild	XX (XX.X)	XX (XX.X)	XX (XX.X)	XX (XX.X)
3 - Moderate	XX (XX.X)	XX (XX.X)	XX (XX.X)	XX (XX.X)
4 - Severe	XX (XX.X)	XX (XX.X)	XX (XX.X)	XX (XX.X)
Week 8, n (%)				
0 - Clear	XX (XX.X)	XX (XX.X)	XX (XX.X)	XX (XX.X)
1 - Almost clear	XX (XX.X)	XX (XX.X)	XX (XX.X)	XX (XX.X)
2 - Mild	XX (XX.X)	XX (XX.X)	XX (XX.X)	XX (XX.X)
3 - Moderate	XX (XX.X)	XX (XX.X)	XX (XX.X)	XX (XX.X)
4 - Severe	XX (XX.X)	XX (XX.X)	XX (XX.X)	XX (XX.X)
Change from baseline				
4 – Worsen by 4 grades	XX (XX.X)	XX (XX.X)	XX (XX.X)	XX (XX.X)
3 – Worsen by 3 grades	XX (XX.X)	XX (XX.X)	XX (XX.X)	XX (XX.X)
2 – Worsen by 2 grades	XX (XX.X)	XX (XX.X)	XX (XX.X)	XX (XX.X)
1 – Worsen by 1 grade	XX (XX.X)	XX (XX.X)	XX (XX.X)	XX (XX.X)
0 – No change	XX (XX.X)	XX (XX.X)	XX (XX.X)	XX (XX.X)
-1 – Improved by 1 grade	XX (XX.X)	XX (XX.X)	XX (XX.X)	XX (XX.X)
-2 – Improved by 2 grades	XX (XX.X)	XX (XX.X)	XX (XX.X)	XX (XX.X)
-3 – Improved by 3 grades	XX (XX.X)	XX (XX.X)	XX (XX.X)	XX (XX.X)
-4 – Improved by 4 grades	XX (XX.X)	XX (XX.X)	XX (XX.X)	XX (XX.X)
Wilcoxon Rank Sum Test, PPC-06 vs. Placebo				
p-value	X.XXXX	X.XXXX	X.XXXX	

<Repeat for Week12, Week16, Week20, Week24>

Note: This analysis excludes subjects with baseline PP PGA score of 0. LOCF = Last Observation Carried Forward.

Generated on XX/XX/XX:XXXX by XXXXX / Uses: XXXX / Reference: Listings XXXX

*Repeat for tables:*

Table 14.2.2.8.3: Analysis of Secondary Efficacy Outcome  
Change from Baseline in Palmoplantar Psoriasis Physician's Global Assessment (PP PGA) by Visit  
Double-Blind Treatment Period  
Full Analysis Set OC

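### The multiply imputed PP PGA table is labelled a Wilcoxon p-value, but its code pools the Hodges-Lehmann shift, which on heavily tied integer changes loses power and can be undefined

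*SAP*

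**What the plan says.** SAP 12.8.2 says of PP PGA: "The change from baseline in severity categories will be compared between treatment groups using a Wilcoxon rank sum test". SAP Section 13 declares this as a change from the protocol: "Wilcoxon rank sum test will be used to compare the change from baseline in PP PGA between treatment groups".

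The shell of Table 14.2.2.8.1 in SAP Section 16 reports one kind of result, headed "Wilcoxon Rank Sum Test p-value, PPC-06 vs. Placebo [1" with the footnote mark at its end. There are three active-arm columns and five visit rows (Weeks 8 to 24), so 3 × 5 = 15 p-values and no effect estimate. The footnote reads "Average based on 50 imputed datasets".

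Below the shell is a directive note, "Use the following syntax to perform Wilcoxon Rank Sum test for MI", followed by two steps:

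1. "Proc NPAR1WAY data=indata Wilcoxon hl", run "By _imputation" on the change variable. The Wilcoxon output is stored in `wilcox` and the Hodges-Lehmann output in `hl`.
2. PROC MIANALYZE on `hl`, with the shift as the effect and its standard error.

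SAP 12.8.1 gives a pooling rule for the co-primary log odds ratios. SAP 12.8.2 gives none for PP PGA, so this note is the only place where the pooling is defined.

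**The concern.** The label and the SAP text promise one test and the code delivers another. The dataset `wilcox` is not read after it is created, so the p-value comes from dividing the pooled shift by its pooled standard error.

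For a continuous outcome the two would usually agree, because the shift estimate comes from inverting the rank sum test. PP PGA change is a small set of integers with most subjects on one or two values. The median pairwise difference can then stay at 0 while the rank sum statistic moves clearly. At stake are 15 p-values published under the name of a test that was not pooled, from a procedure that can miss a real difference or return no p-value.

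**Working it through.** The documents state no sample size, power or error figure for PP PGA, so there is no planned figure to reproduce.

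**Possible values.** The scale is 0–4 (SAP 12.7.2) and subjects with baseline 0 are excluded (note to Table 14.2.2.8.1). Baseline is 1–4 and follow-up 0–4, so change runs from 0 − 4 = −4 to 4 − 1 = +3, which is 8 integers.

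**Worked example.** Assume 40 per arm, with counts at −3/−2/−1/0/+1 of 2/6/14/17/1 (active) and 1/3/8/26/2 (placebo). There are 40 × 40 = 1,600 pairwise differences (active − placebo):

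- Tied at 0: 2·1 + 6·3 + 14·8 + 17·26 + 1·2 = 576.
- Negative (active better): 2·39 + 6·36 + 14·28 + 17·2 = 720.
- Positive: 1,600 − 576 − 720 = 304.

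*Wilcoxon.* U = 720 + 576/2 = 1,008 against 800 expected (Mann-Whitney probability 1,008/1,600 = 0.63). The tied groups are 3, 9, 22, 43 and 3, with Σ(t³ − t) = 90,858. The variance is (1,600/12) × [81 − 90,858/(80 × 79)] = 8,883, so the SD is 94.25. z = (208 − 0.5)/94.25 = 2.20, **p = 0.028**.

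*Hodges-Lehmann.* Ranks 721 to 1,296 are zeros, so the median is 0. The 95% limits are the 597th and 1,004th ordered differences, from 800 − 1.96 × √(1,600 × 81/12) = 596.3, rounded up to 597. They are −1 and 0. SE = (0 − (−1))/(2 × 1.96) = 0.255, shift/SE = 0, **p = 1.00**.

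If the zeros cover both ranks 597 and 1,004, the two limits coincide and SE = 0. The SE formula (interval width over 2 × 1.96) is an assumption about the SAS output.

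**Why more subjects need not help.** Assume most changes are at 0, with active probabilities .05/.15/.35/.42/.03 and placebo .02/.08/.20/.65/.05.

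- P(negative) = .05·.98 + .15·.90 + .35·.70 + .42·.05 = 0.450.
- P(tie) = .001 + .012 + .070 + .273 + .0015 = 0.3575.

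The Mann-Whitney probability is 0.450 + 0.3575/2 = 0.629, a real effect. Because 0.450 < 0.5 < 0.450 + 0.3575, the population shift is exactly 0. The shift test then has nothing to detect.

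**Complete-data simulation** (1,000 datasets per setting). Without an effect, the shift was exactly 0 in 88–100% of datasets and the SE was 0 in 2–100%. With the effect just described:

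| Per arm | Wilcoxon power | Shift-test power |
|---|---|---|
| 20 | 33.7% | 27.7% |
| 40 | 59.4% | 24.0% |
| 80 | 90.2% | 14.6% |

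With a more even spread (active .12/.23/.30/.30/.05, placebo .05/.15/.25/.45/.10), power was 29.5%, 49.1% and 79.2% for Wilcoxon and 27.9%, 42.8% and 44.2% for the shift test.

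**With imputation, as planned** (50 imputations, 40% missing, simple within-arm resampling, Rubin's rules with a t reference):

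- Null rejection of the pooled shift test was about 0–4%. A smaller run of 150 trials per setting gave 0.7–5.3%; its Monte Carlo SE near 5% is √(.05 × .95/150) = 1.8 points.
- The p-value was undefined (zero total variance) in up to 16% of null trials at 20 and 40 per arm, and in up to 62% in a further run that also covered 80 per arm.
- At 80 per arm, power was 9–33%, against 68–74% for the pooled Mann-Whitney probability.
- At 20 and 40 per arm, the pooled shift p-value and the mean of the 50 Wilcoxon p-values differed by more than 0.05 in 73–98% of trials with a defined p-value. The label, code and footnote are therefore not interchangeable.

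**The case against.** **Inflated type I error.** A reader might infer this, because on complete data the shift test rejected in up to 9.5% of null samples at 20 per arm. The planned analysis is pooled, though. Averaging 50 shifts frees the estimate from the integers, and between-imputation variance offsets many zero standard errors. A separate pooled simulation with 25 per arm took complete-data rejection of 7.7–8.8% down to 3.2%. The least favourable setting tried, a wider spread at 25 per arm, went from 14–17% to 5.8–6.0%. The evidence points mainly to conservatism, so a claim of general inflation is not supported.

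**No treatment variable in the code.** This could be read as an undefined comparison. The shell defines it: one column per active arm, each against placebo, one row per visit. A two-sample shift also cannot be computed without a grouping variable, so the omission cannot silently give a wrong p-value. It is a drafting slip.

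**The footnote shows that p-values are averaged.** The code does not do that. The same footnote appears in the MI shells for PASI, BSA, NAPSI, PSSI and NRS, where it belongs to a mean change. It was carried over.

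**Some estimate has to be pooled.** This is true. A Wilcoxon p-value cannot go through Rubin's rules directly, and the shift is a natural companion for continuous data. What fails is its use on heavily tied data. Restoring the CLASS line and correcting the footnote do not repair that.

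**Conclusion.** The point stands as a mismatch between the test named and the quantity pooled, with a real effect on the result. It rests on the text alone that the p-value in Table 14.2.2.8.1 is not a Wilcoxon p-value.

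The size of the effect rests on assumptions: 20 to 80 subjects per arm with palmoplantar disease, illustrative change distributions on −3 to +1, 40% missing, a simpler imputation than the IGA-type model in SAP Section 9, and a standard error taken from the interval width. The documents give neither the subset size nor the distribution. Under these assumptions the pooled test is mostly conservative, loses much of the power of a rank-based test, and sometimes yields no p-value.

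The consequence is small. PP PGA is one secondary endpoint in a subset, tested at an unadjusted 0.05. Its LOCF shell, repeated for the OC tables, shows a direct Wilcoxon p-value. SAP Section 9 names MI as the primary method only for the co-primary endpoints, and those analyses are unaffected.

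**What to change.** In the programming note to Table 14.2.2.8.1:

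1. Run each active-placebo pair at each visit, by imputation, with treatment as the CLASS variable.
2. Pool by Rubin's rules a quantity suited to ordinal data. One choice is the Mann-Whitney probability with its standard error, preferably on the logit scale or with a small-sample correction because it can be slightly liberal at about 25 per arm. The other is the log odds ratio from a proportional-odds model.
3. Relabel the p-value row to match the pooled quantity.
4. Replace the footnote with the pooling rule.

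One sentence in SAP 12.8.2 should state the same rule. The cost is an edit to one programming note, one row label, one footnote and that sentence, made before unblinding. No data collection changes.
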